3.2. Protocol Deviations

Certain protocol deviations are major in that they may affect the ability to assess the safety and efficacy of study drug. Patients with important deviations will be excluded from the PP analysis set. All patients who meet the definition of the FAS analysis set will be included in the FAS analysis set regardless of these deviations.

The criteria for inclusion in the PP set will be finalized and documented prior to unblinding patients in Part 2 of the study.

If a patient is randomized or assigned to a treatment group, but fails to receive treatment, the reason for not receiving treatment will be noted in the CSR. Any such patients who are not

G1 Therapeutics, Inc.
Clinical Study Protocol G1T28-02

Statistical Analysis Plan
Version date: 14Feb2018

treated will be excluded from the FAS, safety, and PP analysis sets but will be included in patients listings for the CSR.

If the wrong treatment is administered to a patient, and the reason for the incorrect treatment is documented, this will be noted in the CSR and the patient's data included in the Safety Analysis Set based on the actual treatment received. A listing of patients whose blind was broken during the study (Part 2) will also be provided in the CSR, if appropriate; data from un-blinded patients will be included in the FAS and excluded from the PP population. Additional protocol deviations will be reviewed in a data review meeting to classify protocol deviations as minor or major, and to discuss the potential impact on statistical analysis.

4. PROSPECTIVELY DEFINED ANALYSES

As outlined in the protocol, trilaciclib is an IV cyclin dependent kinase (CDK) 4/6 inhibitor being evaluated for its ability to decrease chemotherapy-induced myelosuppression when administered in combination with cytotoxic chemotherapy. Unlike granulocyte-colony stimulating factor (GCSF), which stimulates production of neutrophils, and transfusions, which only replace red blood cell (RBC) or platelets, trilaciclib is hypothesized to facilitate myelopreservation of all hematopoietic lineages including neutrophils, RBC, platelets, lymphocytes, etc.

Based on the mechanism of action, it is also hypothesized that the effects of trilaciclib-induced myelopreservation may be more obvious after patients receive repeated rounds of chemotherapy. For example, SCLC patients treated with carboplatin and etoposide often have more dosing delays and hematologic-related adverse events (AEs) after multiple cycles due to repeated damage to the bone marrow. In contrast, addition of trilaciclib to carboplatin and etoposide is theorized to counteract the chemotherapy-induced damage and allow patients to receive multiple cycles of therapy with less dose delays and fewer hematologic-related AEs.

To capture these two aspects of trilaciclib benefit, the following analyses are prospectively proposed in [Table 3](#) and their associated endpoint derivation and analysis methods will be detailed in [Sections 5.1.1 and 6.2.7.1](#).

Table 3 Prospectively Defined Analyses

Proportion of patients with febrile neutropenia during the treatment period
Duration of Grade 4 neutropenia
Duration of Grade 3/4 neutropenia
Average ANC over time (for all cycles; with and without GCSF subset analysis)
Average ANC NADIR over time (for all cycles; with and without GCSF subset analysis)
Average ANC at each scheduled Day 1 of a cycle (for all cycles; with and without GCSF subset analysis)
Average hemoglobin over time (for all cycles)
Average platelet count over time (for all cycles)
Average lymphocyte count over time (for all cycles)
Proportion of patients with RBC transfusions (includes actual or eligible) during the treatment period
Proportion of patients with platelet transfusions (includes actual or eligible) during the treatment period
Proportion of patients with GCSF use during the treatment period
Proportion of patients with ESA use during the treatment period
Proportion of patients with IV antibiotic use during the treatment period
Proportion of patients with infectious SAEs during the treatment period
Proportion of patients with pulmonary infectious SAEs during the treatment period
Time to first major adverse hematologic event (MAHE) which is defined to include components as the following: 
 • hospitalization for a hematologic event (e.g. febrile neutropenia, thrombocytopenia, hemoptysis, etc.) • febrile neutropenia • death related to treatment (including backbone chemotherapy and trilaciclib) • dose delay/reduction due to ANC or platelet counts • duration of Grade 4 ANC > 5 days

G1 Therapeutics, Inc.
Clinical Study Protocol G1T28-02

Statistical Analysis Plan
Version date: 14Feb2018

- RBC transfusion (actual or eligible)
- platelet transfusion (actual or eligible)

ANC = absolute neutrophil count; ESA = erythropoiesis stimulating agent; GCSF = granulocyte-colony stimulating factor; IV = intravenous; NADIR = the lowest point; SAEs = serious AEs.

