  - Incidence of infections overall and by severity
  - Incidence of RBC and platelet transfusions
  - Incidence of hematopoietic growth factors use
  - Incidence and duration of systemic antibiotic use
  
- Exploratory efficacy endpoints:
  - Incidence of Grade 2 or greater nephrotoxicity
  - Incidence of alopecia and mucositis
  - Functional Assessment of Cancer Therapy QOL instrument (FACT) total scale score (general)
  - FACT domain scores (physical, social/family, emotional, and functional well-being)
  - FACT-L total scale score
  - FACT-L lung cancer subscale score
  - FACT-L trial outcome index score
  - FACT-An total scale score
  - FACT-An anemia subscale score
  - FACT-An trial outcome index score
  - Composite hematologic score (this will be specified *a priori* in a SAP)
  - Composite efficacy score (this will be specified *a priori* in a SAP)

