#### 13.4.2.2. Analysis of Hematologic Toxicity Endpoints

The number and percentage of patients with Grade 3 and 4 hematologic toxicities at each cycle and overall during the Treatment Phase will be tabulated for each type of hematologic toxicity and across all type of hematologic toxicities. Percentages for by-cycle summaries will be based on the number of patients treated in the cycle. For tabulations performed based on data collected in Part 2, the difference in rates between treatment groups will be calculated. Two-sided 95% CIs will be constructed around the difference in treatment groups. If there are substantial dose reductions, an incidence rate, adjusting for cumulative exposure, may be reported to account for differing amount of exposure by cycle.

The total number of Grade 3 and 4 hematologic toxicities will be summed over the entire Treatment Phase per patient, separately for each type of hematologic toxicity and across all types of hematologic toxicities. To account for differing amount of exposure, a toxicity rate will be calculated for each patient, and defined relative to cumulative exposure (total number of toxicities divided by cumulative exposure). A recurrent events model may be performed to estimate the incidence of Grade 3 or higher hematologic toxicities and test for the difference between treatment groups.

For each hematologic parameter and cycle, the following shift summaries will be performed: from predose toxicity to maximum ontreatment toxicity; from predose toxicity to end of cycle toxicity; from maximum postdose toxicity to end of cycle toxicity.

Hematologic recovery will be defined in the SAP. The number and percentage of patients with hematologic recovery will be calculated at each cycle. Time to postdose recovery within a cycle will be estimated using the Kaplan-Meier method. A Cox proportional hazard model adjusted for baseline hematologic toxicity and ECOG will also be performed.

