#### 13.4.2.4. Other Efficacy Endpoints

Infections, RBC and platelet transfusions, systemic antibiotic use, and hematopoietic growth factor use will be summarized with the number and percentage of patients experiencing the event any time during the Treatment Phase of the study. For tabulations performed based on data collected in Part 2, the difference between treatment groups will be calculated and reported as described for the incidence of hematologic endpoints.

The number and percent of infections will also be summarized by maximum severity. The infection rate will be calculated as the number of infections occurring during the Treatment Phase divided by cumulative exposure.

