2. STUDY DETAILS

2.1. Study Objectives

The primary, secondary, and exploratory objectives of this study are presented in [Table 1](#).

Table 1 G1T28-02: Study Objectives

	Phase 1b Dose-Finding Portion of Part 1	Phase 2a Expansion Portion of Part 1	Phase 2a Part 2
Primary Objectives			
Assess the DLTs and define the Phase 2 dose of G1T28 administered with E/P therapy	X		
Assess the safety and tolerability of G1T28 administered with E/P therapy	X	X	X
Secondary Objectives			
Assess the PK profile of G1T28	X		
Assess the PK profile of etoposide and carboplatin when administered with G1T28	X		
Assess the hematologic profile (kinetics and incidence/duration/frequency of toxicities) of G1T28 administered with E/P therapy	X	X	X
Assess the incidence of febrile neutropenia	X	X	X
Assess the incidence of infections	X	X	X
Assess the utilization of RBC and platelet transfusions	X	X	X
Assess the utilization of hematopoietic growth factors	X	X	X
Assess the utilization of systemic antibiotics	X	X	X
Assess the incidence of chemotherapy dose reductions and dose interruptions overall	X	X	X
Assess the incidence of Grade 2 or greater nephrotoxicity	X	X	X
Assess tumor response based on RECIST, Version 1.1	X	X	X
Assess PFS and overall survival	X	X	X
Exploratory Objectives			
Assess the incidence of mucositis	X	X	X
Assess the incidence of alopecia	X	X	X
Assess the incidence of fatigue	X	X	X
Assess patient-reported QOL	X	X	X
Assess immunologic markers			X

DLT = dose-limiting toxicity; E/P therapy = etoposide + carboplatin on Day 1 and etoposide on Days 2 and 3 of 21-day cycles; PFS = progression-free survival; PK = pharmacokinetic; QOL = quality of life; RBC = red blood cell; RECIST = Response Evaluation Criteria in Solid Tumors

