5.1.1.7. Infection SAEs and Pulmonary Infection SAEs

Each infection SAE and pulmonary infection SAE is captured in the electronic database. The event terms are coded using the MedDRA Version 20.1. The criterion for identifying the proper infection SAE and pulmonary infection SAEs records is as follows: if the system organ class (SOC) from MedDRA takes value “INFECTIONS AND INFESTATIONS”, the preferred term (PT) takes values from [Table 4](#), and the AE is a serious event.

Table 4 PT List for Grouping Infection AEs and Pulmonary Infection AEs

Category	Preferred terms	
Pulmonary Infection AEs	Bronchitis	
	Influenza	
	Pneumonia	
	Pneumonia bacterial	
	Respiratory tract infection	
	Upper respiratory tract infection	
	Viral upper respiratory tract infection	
Infection AEs	Anal abscess	Oral herpes
	Bacteraemia	Pharyngitis streptococcal
	Bronchitis	Pneumonia
	Candida infection	Pneumonia bacterial
	Chronic sinusitis	Respiratory tract infection
	Conjunctivitis	Sepsis
	Infection	Skin infection
	Influenza	Upper respiratory tract infection
	Nasopharyngitis	Urinary tract infection
	Oral candidiasis	Urosepsis
		Viral upper respiratory tract infection

A cycle is considered to have an infection SAE if any date between the start and stop date of the AE overlaps with any date between the start of cycle and end of cycle. If an event ends on the

cycle start day, it will not be counted as an event in that cycle unless the event also started on that day. For the treatment period, the total number of infection SAE events is the number of cycles where at least one infection SAE is observed. If a patient did not have any infection SAE events, the value of 0 will be assigned to that patient. Data handling conventions for missing start and stop dates for AEs are described in [Section 5.2.1](#).

Any occurrence of an infection SAE during the treatment period is defined as a binary variable (Yes or No); Yes if total number of infection SAE events ≥ 1 is observed, No for other scenarios.

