6.2.7. Efficacy Analyses

All the efficacy variables will be summarized using descriptive statistics by cycle or visit, with the supportive data provided in patient listings. Part 1 will be summarized using only descriptive statistics. For Part 2, in addition to the descriptive summary, the between treatment comparison (trilaciclib vs placebo), if applicable, will be performed only for those prospectively-defined endpoints outlined in [Section 5.1.1](#). For these comparisons, all statistical tests will be conducted at a two-sided significance level of 20% unless otherwise specified. Where appropriate, model-based point estimates, together with their two-sided 80% CIs will be presented along with the two-sided p-value for the test. Graphical presentation of efficacy results will be appropriately performed as needed.

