6.2.8. Safety Analyses

All safety analyses will be based on the safety analysis set, as defined in [Section 3.1.2](#). Descriptive statistics will be used to summarize the safety outcomes. The continuous safety variables will be summarized at each visit including end of each cycle (the last non-missing assessment during the cycle), end of treatment (the last non-missing assessment during the treatment period), and end of study (the last non-missing assessment during the whole study), if applicable. No inferential analyses of safety data are planned unless otherwise specified.

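### The SAP compares arms only on serious infections; the protocol's Part 2 difference with 95% CI for any infection is dropped, and SAP Section 7 does not list this

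*SAP*

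**What the plan says.** Protocol Table 5-1 and SAP Table 1 (Section 2.1) give the same secondary objective for every portion of the study, including Part 2: "Assess the incidence of infections". Neither limits it by seriousness or grade.

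Protocol 13.4.1 lists the endpoint as "Incidence of infections overall and by severity". Protocol 13.4.2.4 counts patients with an infection at any time in the Treatment Phase and adds that, for Part 2, "the difference between treatment groups will be calculated and reported as described for the incidence of hematologic endpoints". The section it points to, 13.4.2.2, states: "Two-sided 95% CIs will be constructed around the difference in treatment groups".

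SAP Table 3 (Section 4) has "Proportion of patients with infectious SAEs during the treatment period" and a matching row for pulmonary infections. SAP 5.1.1.7 selects events by the infections organ class, by a list of preferred terms (Table 4), and by the condition "and the AE is a serious event". SAP 6.2.7 says that between-arm efficacy comparison "will be performed only for those prospectively-defined endpoints outlined in" Section 5.1.1. For AE tables, SAP 6.2.8 says: "No inferential analyses of safety data are planned unless otherwise specified". SAP Section 7 lists the analyses removed from the protocol. Two of them concern infections: the summary by maximum severity and the rate per cumulative exposure.

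**The concern.** The SAP keeps the objective as worded but changes the quantity on which the arms are compared. Seriousness and severity are different axes: protocol 11.3.1.2 says that seriousness rests on outcome or action criteria, not on intensity. An infection that meets none of those criteria scores as no event in the SAP's infection comparison, whatever its grade.

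The comparison therefore answers a narrower question than the stated objective. The protocol's effect estimate for that objective is lost, and a reader who uses Section 7 to learn what was dropped would conclude that the overall infection comparison stands as planned.

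**Working it through.** This is a check of text against text. The only arithmetic concerns the precision that a restored estimate would have.

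**Side-by-side reading**

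1. *Population of events.* Protocol: any infection in the Treatment Phase. SAP: infections in the organ class, on the Table 4 list, and serious. The SAP set is a subset.
2. *Between-arm estimate.* Protocol: difference in proportions with a two-sided 95% CI. The cross-reference in 13.4.2.4 is loosely worded, but protocol 13.2.3 also sets 95% as the default, so the level is not in doubt. SAP 6.2.7.1: ECOG-stratified, CMH-weighted difference with an 80% CI and an exact CMH p-value, for infection SAEs and pulmonary infection SAEs only.
3. *Is any infection compared elsewhere?* SAP 6.2.7 limits efficacy comparisons to Section 5.1.1, which has no such endpoint. SAP 6.2.8.1 tabulates all treatment-emergent AEs by organ class and/or preferred term and by CTCAE grade, and SAP 6.1.1 presents all tables by treatment group. Per-arm counts are therefore available, but with no difference or interval.
4. *Do other compared endpoints cover the gap?* Only in part. Febrile neutropenia and IV antibiotic use are compared. A non-serious infection treated with oral antibiotics enters neither the infection comparison nor the IV antibiotic comparison.
5. *Is the change declared?* Section 7 names the maximum-severity summary and the exposure-adjusted rate. It does not name the overall infection difference or the restriction to serious events.

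**Precision**

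Input: 70 patients randomized 1:1, so n = 35 per arm (protocol 13.1, SAP 2.3).

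- The plan's own figure, the largest Wilson 95% half-width for one arm, is z·√[p(1−p)/n + z²/(4n²)] / (1 + z²/n) at p = 0.5 and z = 1.96. This is 1.96 × √(0.007143 + 0.000784) / 1.10976 = 0.157, which agrees with the stated 0.157.
- For a difference between two arms, the largest unadjusted Wald half-width is z·√(0.25/35 + 0.25/35) = z × 0.1195. At 95% this is 1.96 × 0.1195 = 0.234. At 80% it is 1.2816 × 0.1195 = 0.153.

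These are upper limits under p = 0.5. They use no infection rate and make no claim about the size of any effect.

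**The case against.** The strongest reply is that the objective is still met. It asks for incidence, not for an effect estimate, and incidence by arm and by worst grade is in the AE tables. The windows are also close: treatment-emergent AEs run to 30 days after the last dose (Day 3 + 30 = Day 33 of the last cycle if all doses are given), and the SAP treatment period runs to Day 36. The full analysis set and the safety set both require one dose, so in Part 2 they differ little. An unadjusted difference could be worked out from the reported counts. Serious infection is also a reasonable choice for a small study sized on clinical grounds, it is stated openly in SAP Table 3, and the SAP says its decisions were made before database lock.

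Most of this stands. It narrows the point to one missing estimate with its interval and one missing line in Section 7. It does not remove the point, because the protocol specified that estimate and the SAP drops it without saying so.

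Section 7 also says it is keyed to Protocol Amendment 7 (11 May 2016), whose text is not available here, while the SAP introduction cites Version 8 (15 September 2016). The supplied protocol still contains the overall infection endpoint, so this explains at most how the omission arose.

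A reader might infer more than the documents support:

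- *That the infection objective has no between-arm analysis.* It has one, for serious infections.
- *That Section 7 is silent on infections.* It declares two infection-related removals.
- *That most of the infection information is lost, or that power falls by a given amount.* The documents give no rate for serious or for all infections, so any such figure would come from assumed inputs.
- *That serious simply means hospitalized.* Protocol 11.3.1.2 also covers death, life-threatening events, disability and important medical events.
- *That a Grade 3 or higher infection comparison is owed.* The protocol plans no such between-arm endpoint.

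**Conclusion.** The point holds in limited form. The SAP compares arms only on infection SAEs and pulmonary infection SAEs, drops the protocol's Part 2 difference with 95% CI for any infection, and does not list this in Section 7. Its size is one protocol-specified effect estimate for one secondary objective. No magnitude beyond that is claimed. With 35 per arm, the restored difference would have a 95% half-width of at most about 0.234 before adjustment for ECOG, so it would be descriptive, in keeping with protocol 13.2.3.

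The conclusion rests on the supplied protocol being the text that the SAP implements. It should be corrected because the remedy is cheap and lets the trial report on the objective that it states; it does not undermine the rest of the plan.

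**What to change.** - In SAP 5.1.1.7, add one binary endpoint: occurrence of any infection AE during the treatment period, defined as any event in the MedDRA class Infections and Infestations, serious or not, without the Table 4 term filter.
- In SAP 6.2.7.1, give it the existing ECOG-stratified, CMH-weighted difference with the protocol's 95% CI. An 80% CI may be shown alongside for consistency with the other rows.
- Leave the two serious-infection endpoints as they are, and state in Section 7 that they were added to the protocol's endpoints.

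The cost is a few lines of text and one more run of a method already planned, on AE data already collected and coded. The downside is that the eight binary endpoints in 6.2.7.1 become nine, in a list for which the SAP describes no multiplicity adjustment. Report the new one as an estimate with its interval rather than as a test.

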5. PRIMARY AND SECONDARY ENDPOINTS

The following general definitions will be applied to all endpoints derivation unless otherwise specified.

Term	Definition
Grade 4 neutropenia	ANC lab value that meets the common terminology criteria for adverse events (CTCAE) criteria for \geq Grade 4 toxicity
Grade 3/4 neutropenia	ANC lab value that meets the CTCAE criteria for \geq Grade 3 toxicity
Cycle baseline	The last non-missing value within the window starting from 3 days prior to the date/time of study drug administration on Day 1 of Cycle 1 and 1 day prior to Day 1 of each subsequent cycle (i.e. Cycle 2, Cycle 3, etc); must be prior to the time of study drug administration
Cycle NADIR	The lowest value for a given hematologic parameter that occurs between start of cycle and end of cycle and is less than the cycle baseline.
Duration of cycle	Total number of days from start of cycle to end of cycle, that is, date of end of a cycle - date of start of cycle + 1.
End of cycle*	Day 1 of the subsequent cycle. For example, the end of cycle for Cycle 1 is Day 1 of Cycle 2. For the last cycle (where no subsequent cycle is given), the end of cycle will be defined as Day 36.
Start of cycle	Day 1 of each cycle starts with the administration of study drug(s) (etoposide, carboplatin or trilaciclib)
Start of study	Day 1 of Cycle 1
Study baseline	The last non-missing value prior to, or on the date of administration of study drug(s) (etoposide, carboplatin or trilaciclib); must be prior to the time of study drug administration
Change from baseline	Calculated as the post-baseline value minus the baseline value. If the baseline value is missing for a particular endpoint, change from baseline will be missing.
Treatment period	Total number of days from start of cycle for Cycle 1 and end of cycle for the last cycle

* For various hematologic parameter analyses, the last assessment prior to end of cycle will be utilized in the analyses. Situations where this applies will be indicated as such.

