5.1. Efficacy endpoints

5.1.1. Primary Prospectively-Defined Clinical Endpoints for Efficacy

5.1.1.1. Febrile Neutropenia AEs

A cycle is considered to have a febrile neutropenia AE if any date between the start and stop date of the AE overlaps with any date between the start of cycle and end of cycle. If an event ends on the cycle start day, it will not be counted as an event in that cycle unless the event also started on that day. For the treatment period, the total number of febrile neutropenia AE events is the number of cycles where at least one febrile neutropenia AE is observed. If a patient did not have any febrile neutropenia AE events, the value of 0 will be assigned to that patient. AEs during the study is captured in the electronic database. The event terms are coded using the Medical Dictionary for Regulatory Affairs (MedDRA Version 20.1) and "FEBRILE NEUTROPENIA" is

a preferred term which can be used to identify the proper AE records. Data handling conventions for missing start and stop dates for AEs are described in [Section 5.2.1](#).

Any occurrence of a febrile neutropenia AE during the treatment period is defined as a binary variable (Yes or No); Yes if total number of febrile neutropenia AE events ≥ 1 is observed, No for other scenarios.

5.1.1.2. **RBC Transfusions**

Within a cycle, a RBC transfusion event is defined as either (1) an actual RBC transfusion, OR (2) eligible for RBC transfusion = hemoglobin < 8.0 g/dL. Therefore, for the treatment period, a total number of RBC transfusions (i.e. a RBC transfusion event = Yes) is obtained as the number of cycles in which there is at least one RBC transfusion event. If a patient did not have any RBC transfusion events, the value of 0 will be assigned to that patient. Hence, the total number of cycles without RBC transfusion is calculated as the total number of treatment cycles received – total number of cycles with RBC transfusion.

To define those cycles where a patient was eligible for a RBC transfusion, the lab value of hemoglobin (< 8.0 g/dL) must fall between start of cycle and end of cycle for that cycle. Any unscheduled data and the actual assessment date (rather than visit date) will be included in the derivation.

Hence, any occurrence of a RBC transfusion during the treatment period is defined as a binary variable (Yes or No); Yes if total number of cycles with RBC transfusion ≥ 1 is observed, No for other scenarios.

5.1.1.3. **Platelet Transfusions**

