[c] Hematology may be obtained up to 3 days prior to first dose of G1T28/placebo + EP therapy in Cycle 1, and 1 day prior to first dose for subsequent cycles.

[d] Patient-reported outcomes should be completed at Days 1 and 10 of each cycle and at the Post-Treatment Visit. If a cycle is delayed, the patient should still complete the PRO on the scheduled Day 1 of the next cycle, as well as the actual first dosing day of the next cycle of G1T28 or placebo + E/P therapy. Patient-reported outcomes may be obtained up to 24 hours prior to the first dose of each cycle of G1T28 or placebo + E/P therapy.

[e] 60 ± 7 days after the post-treatment visit only for hematologic parameters and immunologic biomarker. The data is collected only for patients in Part 2.

[f] If Day 1 is included in the windowing, the associated assessment must be post G1T28 infusion.

Note: The end date of a cycle (EOC) is defined as the date of Day 1 study drug administration of its next cycle. For the last cycle (where no subsequent cycle is given), the end of cycle will be defined as Day 36 relative to the first dose of the cycle. Hence, for the last cycle, the window for EOC is 19-36.

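### The SAP places each dosing Day 1 after the first in two cycles, so some Day 1 events count twice in descriptive per-cycle summaries; no tested endpoint changes

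*SAP*

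**What the plan says.** **Boundaries.** The general definitions in SAP Section 5 state that "the end of cycle for Cycle 1 is Day 1 of Cycle 2". A cycle begins on its Day 1 with study drug, and the last cycle ends on Day 36. Cycle duration is "date of end of a cycle - date of start of cycle + 1". The note to Table 20 in SAP 6.1.3 repeats the rule: "The end date of a cycle (EOC) is defined as the date of Day 1 study drug administration of its next cycle".

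**Assignment of events to cycles.**
- Laboratory events go by actual assessment date. For RBC transfusion eligibility (SAP 5.1.1.2), "the lab value of hemoglobin (< 8.0 g/dL) must fall between start of cycle and end of cycle for that cycle". Platelets (5.1.1.3) are worded alike, and creatinine (5.1.2.1) is also counted per cycle on the actual date.
- G-CSF, ESA and IV antibiotics (5.1.1.4 to 5.1.1.6) count in any cycle whose dates overlap an administration date.
- Febrile neutropenia and infection SAEs (5.1.1.1, 5.1.1.7) also go by date overlap, with one tie-break: "If an event ends on the cycle start day, it will not be counted as an event in that cycle", unless it also began that day.

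**Use.** Each total is the number of cycles with at least one event. For transfusions, G-CSF, ESA and antibiotics, cycles without an event are obtained by subtraction from cycles received. Each total is then reduced to yes/no for the treatment period. SAP 6.2.7 adds: "All the efficacy variables will be summarized using descriptive statistics by cycle or visit".

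**The concern.** Consecutive cycles share a calendar day, and that day is busy: it is the dosing visit, with scheduled blood tests. Only adverse events have a boundary rule, and it works in one direction. It removes an event that ends on Day 1 from the new cycle, but does not remove an event that starts on Day 1 from the old one. Laboratory values, transfusions and drugs have no rule.

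What is at stake is the accuracy of the by-cycle tables and of the totals of cycles with and without an event. Readers will look at these tables because SAP Section 4 expects that the "effects of trilaciclib-induced myelopreservation may be more obvious after patients receive repeated rounds of chemotherapy". Crediting one event to two adjacent cycles blurs that picture. The result can also depend on scheduling. Hematology may be drawn up to 24 hours before dosing, so the same predose value counts once if drawn the day before and twice if drawn on the day.

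**Working it through.** **Inputs.** 21-day cycles (SAP Table 1 footnote); start, end, Day 36 and duration rules (SAP 5); exposure formula (SAP 5.1.3.1); hematology on Days 1, 3, 8, 10 and 15 of each cycle plus Day 22 of the last (Protocol Table 9-1). The example is six on-time cycles starting on study days 1, 22, 43, 64, 85 and 106.

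**Cycle length.** The plan's 21 days is not reproduced by its own duration formula: 22 − 1 + 1 = 22 days. The last cycle has 36 days and ends on study day 106 + 35 = 141.
- Sum of cycle durations: 5 × 22 + 36 = 146 days.
- Treatment period: 141 − 1 + 1 = 141 days.
- Days counted twice: 146 − 141 = 5, one per boundary.
- SAP 5.1.3.1, by contrast: 106 − 1 + 21 = 126 = 6 × 21.

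**Assignment under the rules as written.**

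| Record | Cycles credited |
|---|---|
| Hemoglobin < 8.0 g/dL or RBC transfusion on Cycle 2 Day 1 | 1 and 2 |
| One-day drug use on Cycle 2 Day 1 | 1 and 2 |
| Adverse event from Cycle 2 Day 1 to Day 5 | 1 and 2 |
| Adverse event starting and ending on Cycle 2 Day 1 | 1 and 2 |
| Adverse event from Cycle 1 Day 18 to Cycle 2 Day 1 | 1 only (tie-break works) |
| Hemoglobin < 8.0 g/dL on Cycle 2 Day 8 | 2 only |

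A patient with two cycles and a single RBC transfusion event, on Cycle 2 Day 1, is recorded as two cycles with and none without. With each record counted once, it is one and one.

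**Illustrative size, both under assumptions.**
- One-day events spread evenly over 141 days: 146/141 = 1.035, about +3.5%.
- Scheduled draws: 6 × 5 + 1 = 31, of which 5 are shared, giving 36 cycle memberships. If each draw is equally likely to be the only qualifying one: 36/31 = 1.161, about +16%. This is an upper figure, because there is no inflation when the neighbouring cycle already has a qualifying event.

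**Any-occurrence endpoints.** A record that falls in at least one cycle under one rule does so under the other. A simulation of 20,000 patients comparing the two rules gave 0 differences.

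**The case against.** **No test uses the counts.** This stands. The eight binary endpoints in SAP 6.2.7.1 need only one event in the treatment period, MAHE uses first-event dates, and nephrotoxicity is descriptive. A reader might infer that the shared day undermines the test of whether benefit grows over cycles. It does not: the analyses in SAP Table 3, which are meant to capture that benefit, contain no per-cycle event totals.

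**Cycle-start criteria.** A reader might also infer that the arm with more Day 1 cytopenia is hit harder. The documents do not support this for neutrophils or platelets. The shared day is the actual dosing day, which requires ANC ≥ 1.5 and platelets ≥ 100 × 10⁹/L. Unrecovered patients are delayed, so their scheduled Day 1 is not the shared day. Protocol 8.4.4.2 places indicated G-CSF no earlier than Day 4. The criterion for drug-related nonhematologic toxicity also limits creatinine events. Hemoglobin is not a start criterion, so RBC transfusion events remain the clearest exposure.

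**An exclusive reading.** The SAP's word for the interval could be read as excluding its end points. The +1 in the duration formula and the existence of an adverse-event tie-break both tell against that. A predose value could also be read as preceding the new cycle, which begins with drug administration. The laboratory rules go by date, however, so the text does not settle it. The Section 5 footnote on using the last assessment before end of cycle applies only where indicated, and the event counts do not invoke it.

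**Moving the cycle end would do harm.** This stands and shapes the fix. In a non-final cycle the next scheduled hematology after Day 15 is the next Day 1. Neutropenia duration and its censoring (SAP 5.1.1.8, 5.1.1.9) and the end-of-cycle visit window (6.1.3) depend on that date.

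**Conclusion.** The rule is wrong as written, with limited impact. The double assignment follows from the SAP's own definitions. It overstates cycles with an event, and understates cycles without, in descriptive summaries only. The practical exposure is Day 1 hemoglobin below 8.0 g/dL, RBC transfusions, ESA and IV antibiotic doses, creatinine, and adverse events starting on Day 1.

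The illustrative range is about 3.5% to 16%, under the two assumptions shown, for six on-time cycles. A reader might suppose that 10 to 40% of events fall on a dosing Day 1 and that totals are inflated to match. Neither document gives such a share, and the role of Day 1 blood tests as a pre-treatment check would not carry over to transfusions, drugs or adverse events. The 22-day cycle length is an internal inconsistency with no shown effect on exposure or dose intensity, which use the formula in SAP 5.1.3.1.

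**What to change.** Keep the end-of-cycle definition for neutropenia duration, censoring and the end-of-cycle visit window. Add a tie-break for event counting only, so that each Day 1 record counts in one cycle:
- Adverse events and drugs that start on Day 1 count in the new cycle only.
- A predose Day 1 laboratory value and any same-day transfusion count together in one pre-specified cycle. Splitting them would still count a low hemoglobin and its transfusion in two cycles. Choosing the ending cycle would also treat a predose value alike whether drawn that day or the day before.

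Correct the duration formula. For a non-final cycle, drop the +1, so that an on-time cycle is 22 − 1 = 21 days. Keep it for the last cycle (36 days). The six durations then sum to 5 × 21 + 36 = 141, equal to the treatment period and in line with SAP 5.1.3.1.

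Set the rule before Part 2 is unblinded. The cost is one SAP sentence and minor programming, with no new data.
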